1

Research protocol

4th National Registry of Cardiovascular Surgery (CCV) in Argentina

-Version N ° 3- 8 of JULY 2021

Page 2

2

Confidentiality notice: The concepts and information included in this document are confidential and exclusive and not they must be disclosed in whole or in part without the express written consent of the coordinator.

Page 3

3

PROTOCOL SUMMARY

> Title

1- Prospective registry of patients undergoing CCV in Argentina

> Study Phase

1- Prospective Registry (IV)

> Evaluation

1- Follow-up of patients during hospitalization and 30 days after surgery.

> Primary Objectives

^{1.a.}

Determine the evolution and surgical complications in patients undergoing CCV

^{1.b.}

To determine the association between different risk variables during the intranosocomial stay and at 30 days of discharge including nosocomial readmission during the 30-day follow-up.

> Secondary Objectives

To determine the association between different variables that occurred before, during and after the surgical intervention.

To determine the association between different variables of risk at discharge and the rate of complications, including

mortality and readmissions during the 30 days following discharge, such as:

Cardiovascular mortality, all-cause mortality, rehospitalization, infectious complications.

To determine the association between different variables with cardiovascular mortality in relation to CCV.

Assess eventual complications 30 days after hospital discharge

Page 4

4

> Study Design

National, multicenter, analytical, prospective cohort study for prognostic evaluation in patients undergoing cardiovascular surgery (CCV)

> Sample Size

The largest number of patients (between 2000 and 3000) will be enrolled during a set period of time (1 year), from

October 1, 2020 to September 30, 2021

> Eligibility Criteria

Over 18 years

Myocardial revascularization surgery

Valvular surgeries

Ascending Aortic Surgery

Type A Aortic Dissection Surgery

Combined surgery

➤ **Exclusion Criteria**

Cardiovascular surgery for congenital pathologies

Peripheral vascular surgery

Cardiovascular surgery secondary to trauma

Thoracic and abdominal aorta pathology

Other surgeries

➤ **Procedures**

Various centers are included nationwide with a CCV service capable of admitting and intervening patients with criteria already established.

They are arranged below:

Leben Health

Private Hospital Santa Clara de Asis

[name] Hospital

Pasteur Clinic

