The principal investigators of the study are:

[name]

[name]

It will be assigned during the inclusion of investigator patients for each of the centers, who will be responsible for completing the form (*CRF*) and sending the registered data.

7

Additional Information

Introduction

More than ten years have passed since the last CCV registration in the Argentine Republic

In recent decades, the evolution of CCV has shown a reduction in the rate of complications and mortality in centers

specialized

objectives

Record

1. determine complications, mortality and hospital stay, as well as evolution at 30 days after CVD

In our country

2. Compare our variables with those exposed by the different international scores and thus be able to predict the

estimated evolution of our patients.

Substudy

1. Determine the association between different variables, complication rate and mortality 30 days after discharge.

Proposed design

The study consists of **2 stages** , with the voluntary participation of the different centers, which is divided into nosocomial phase and phase a

30 days after discharge

Prospective multicenter registry of prognostic correlation with various risk scores in patients undergoing CCV and

evolution of the same 30 days after discharge

Material and methods

Patients who meet the eligibility criteria described above are included from October 1, 2020

The protocol consists of 2 stages:

1) Nosocomial Phase: a descriptive record is made of the referred variables and the risk parameters upon discharge from

the patients

2) 30 days after discharge, the respective forms will be filled out for the final evaluation of patients who have undergone CCV and discharged from participating institutions

8

Specific Protocol (Operational Definition of Variables):

A complete clinical history of the patient is taken (according to usual practice) and the data is filled out in the Pre, Intra and Post-surgical stage according to what is established in the form

Affiliate Information and Background

Record ID _____

Date of admission _____

Acronyms for Name and Surname _____

Last 3 digits of document number _____

(Last 3 digits only)

Age _____ gender _____ Weight (kg) _____ Height (cm) _____

Public Hospital Coverage

PAMI

Social work

Prepaid

Particular

Telephone

Phone 2 _____

Email _____

Background

Arterial hypertension Yes No

Diabetes Yes No

Diabetic retinopathy Yes No

Dyslipidemia Yes No

Ex-smoker tobacco

I never smoke

Smokes daily

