Atrioventricular block Yes No
Complex ventricular arrhythmia Yes No
Transient pacemaker Yes No
Permanent pacemaker Yes No
I do prophylaxis for postoperative AF Yes No
Drug used

POP day of initiation of prophylaxis for AF

Renal failure Yes No
(Increase in creatinine above 50%
with respect to the baseline value and / or

17

hemodialysis)

Hemodialysis Yes No

Stroke Yes No

(Focal and / or diffuse brain injury confirmed by clinical findings and / or computed tomography with sensory or motor sequelae upon discharge of the patient)

Transient ischemic accident Yes No

Psychiatric disorders Yes No

(Any of the following: delirium, hallucinations, psychomotor arousal)

Required treatment with ... Risperidone

Quetiapine

Haloperidol

Other

Respiratory distress syndrome Yes No

(Infiltrate in 4 quadrants - PCP <18 - PAFI <200)

Fever without obvious focus Yes No

Sepsis Yes No

(Suspected or documented infection with dysfunction of target organ and at least two of the following criteria: Temperature > 38 ° C or <36 ° C, White blood cell count greater than 12,000 uL or less at 4000 uL, Tachycardia, Tachypnea > 30 rpm, Altered mental state, Positive culture of primary focus of infection, mean arterial pressure less than 70 mm Hg for a minimum fingers

hours, poor distal perfusion ("))

Urinary infection Yes No

Respiratory infection Yes No

Surgical wound infection Yes No

Superficial wound infection Yes No

Saphenous wound infection Yes No

Sternal infection Yes No

Mediastinitis Yes No

Sternal reopening requirement Yes No

Sternal reopening POP day

Sternal mechanical instability Yes No

COVID-19 infection development during internment

18

If not

TOTAL days of hospitalization until discharge

POSTOPERATIVE days until discharge

Discharge

Alive

Dead _____

Death cause:

Infectious

Cardiovascular

Distributive shock

Hemorrhage

Cardiac tamponade

Stroke

Respiratory distress

Multi-organ failure

Another cause

Death from infectious cause: Mediastinitis Pneumopathy Sepsis Other

Identified germ

Death from cardiovascular cause: Myocardial infarction Arrhythmia Heart failure

Pre Registration Laboratory

Hematocrit _____ Blood glucose _____

Uremia _____ Creatinine _____

Medication at discharge ASA

Clopidogrel

Ticagrelor

Prasugrel

Statins

Beta-blockers

Sartan

ACE inhibitors

Loop diuretic

Thiazide

Spironolactone

Insulin

Oral hypoglycemic

Anticoagulants

Investigator Notes

19

Follow-up

Re-internment Yes No

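### The 30-day follow-up form records infection only as a cause of re-admission, so the named post-discharge outcome of infectious complications will be under-counted

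*Protocol*

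**What the plan says.** In the Protocol Summary, one secondary objective relates risk variables at discharge to the rate of complications, and then continues "mortality and readmissions during the 30 days following discharge, such as". The list that follows is "Cardiovascular mortality, all-cause mortality, rehospitalization, infectious complications". A further secondary objective reads "Assess eventual complications 30 days after hospital discharge". The Substudy under Additional Information has a similar aim: "Determine the association between different variables, complication rate and mortality 30 days after discharge".

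Under Material and methods, the post-discharge data come from forms completed 30 days after discharge. The Follow-up form opens with "Re-internment Yes No" and then gives:

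- the cause of re-admission: cardiac, respiratory or renal failure, sepsis, or other;
- for sepsis, the starting focus;
- a line for any other cause of re-admission;
- death within 30 days of discharge, classed as cardiovascular or not.

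The hospital form is much fuller. Its Postoperative part has separate yes/no items for several infections and one for "COVID-19 infection development during internment". Its cause-of-death part has an infectious branch: "Death from infectious cause: Mediastinitis Pneumopathy Sepsis Other".

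**The concern.** The objectives promise infection after discharge as an outcome in its own right, but the form collects it only through re-admission. Wound, urinary and respiratory infections can be treated without a new admission, and such cases would leave no trace in the data.

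Two things are at stake. First, the reported post-discharge infection rate would be too low. Second, the infection outcome would be largely a subset of rehospitalization, so the two would not be measured independently. An association between a risk variable and infection would in fact be an association with being re-admitted for infection. No analysis plan can repair this, because the data are never collected.

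**Working it through.** **1. Objectives against form.** The protocol states no figure to reproduce, so the check sets the items side by side.

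| Event after discharge | Where the Follow-up form records it |
|---|---|
| Sepsis leading to re-admission | Named cause, with focus |
| Non-septic infection leading to re-admission | Under other, identifiable only if the site writes it in |
| Infection treated without re-admission | No field |
| Infectious death without re-admission | Non-cardiovascular death, not separable |

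Infection items asked independently of re-admission number 0 on the Follow-up form. The hospital form has 8 (sepsis, urinary, respiratory, surgical wound, superficial wound, saphenous wound, sternal, mediastinitis), plus COVID-19.

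**2. Direction and size of the under-count.** Let p be the true 30-day infection risk, f the share of infections identifiable through a re-admission cause, and N the number of patients. Then recorded = N × p × f, and the share missed = 1 − f whatever p is. It is zero only if every infection leads to a re-admission recorded with its infectious cause.

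The protocol gives neither p nor f. Purely as illustration, assume p = 5% and use the planned enrolment of 2000–3000 as N. True infections are then 100–150.

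| Assumed f | Recorded | Share missed |
|---|---|---|
| 25% | 25–38 | 75% |
| 50% | 50–75 | 50% |
| 75% | 75–113 | 25% |

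**3. How many patients a new form could still reach.** Inputs from the protocol are the enrolment window, "October 1, 2020 to September 30, 2021" (365 days), the version date of 8 July 2021 (280 days after 1 October 2020), and follow-up at 30 days after discharge. Assumptions are even enrolment, a stay of 5 to 14 days, and a lead time of 0, 30 or 60 days before the new form is in use.

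Share already followed = (280 + lead − 30 − stay) / 365. The share still reachable is the remainder.

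| Lead | Already followed, stay 5 d | Already followed, stay 14 d | Still reachable | Of 2000–3000 patients |
|---|---|---|---|---|
| 0 d | 245/365 = 67.1% | 236/365 = 64.7% | 32.9–35.3% | 658–1060 |
| 30 d | 275/365 = 75.3% | 266/365 = 72.9% | 24.7–27.1% | 493–814 |
| 60 d | 305/365 = 83.6% | 296/365 = 81.1% | 16.4–18.9% | 329–567 |

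These figures describe the reach of one remedy. They do not measure the size of the bias.

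**The case against.** The best counter-argument is that the form is itself the definition. The protocol presents its data forms as the operational definition of its variables, so the 30-day infectious outcome could simply mean re-admission for sepsis or another infection the site records. On that reading nothing is under-counted and only the label is too broad. The wording before the list could also confine it to deaths and re-admissions. Overlapping entries prove little, since cardiovascular mortality lies within all-cause mortality in the same list.

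This reading is possible but fits poorly. The objective concerns the rate of complications, with mortality and re-admission given as inclusions, and a separate objective covers complications at 30 days in general. Even if the narrow reading is intended, the objectives need to say so.

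Other points:

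- **Layout.** The extracted text shows no branching, so the sepsis line might stand alone. It sits between two re-admission lines, which makes that unlikely, and it would still cover sepsis only.
- **Other forms.** The protocol speaks of follow-up forms in the plural, but shows no other.
- **Cause of death.** The two-way split does serve the two mortality outcomes named. Losing infectious deaths matters only for the infection outcome.
- **Reach.** The Evaluation entry of the Protocol Summary counts 30 days from surgery. On that anchor, with enrolment dated at surgery, the zero-lead ceiling is 1 − 250/365 = 31.5%. The conclusion does not change.
- **Cost.** A new item brings more than a tick box: two ascertainment rules within a one-year cohort and split reporting. This stands, and it favours restating the outcome if few patients remain to be followed.

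**Conclusion.** The concern holds. As printed, the Follow-up form cannot deliver post-discharge infectious complications as an outcome distinct from re-admission. The bias is downward. Its size cannot be derived from the protocol, and the 5% risk and 25–75% capture shares above are assumptions used only for illustration. The conclusion rests on reading the objective as covering infections whether or not they led to re-admission, which its wording supports better than the narrower reading. It also rests on there being no further follow-up form beyond the one shown.

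This affects one named secondary outcome. Re-admission and mortality, the other outcomes in the list, are collected. The correction is cheap and should be made.

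**What to change.** Choose one of two changes.

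1. **Change the form.** Add one infection yes/no item asked of every discharged patient, including those who died, regardless of re-admission. Take the type list from the hospital form's existing infection items, ask whether the infection led to re-admission, and record the date the new form came into use. For the whole cohort, report re-admission for sepsis, or for infection where the site wrote it in. Report any post-discharge infection only for patients followed on the new form. The data-entry cost is small, but ascertainment changes mid-study and this must be reported. The item reaches at most about a third of patients, or 16–27% with a 30–60 day lead, under the assumptions above.

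2. **Restate the outcome.** If the form is not changed, or follow-up is already largely complete, reword the objective as re-admission for sepsis or other recorded infection, and note that non-septic infections depend on what sites write in. This costs one sentence and works at any date, but gives up post-discharge infection as an outcome.

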(Within the first 30 days after discharge)

Cause of re-admission:

Heart failure

Respiratory insufficiency

Renal insufficiency

Sepsis:

Other

Sepsis Yes: Sepsis starting point: Mediastinitis or other focus

Another cause of re-admission

Death no

Death Yes:

(Within the first 30 days after discharge)

Cause of death in follow-up: Cardiovascular- NON-cardiovascular cause

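### The 30-day objectives promise complications, including infections, but the follow-up form records only re-admission by cause and death

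*Protocol*

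**What the plan says.** The Protocol Summary, under Secondary Objectives, ties a complication rate to the 30 days following discharge and lists four outcomes: "Cardiovascular mortality, all-cause mortality, rehospitalization, infectious complications". Infection stands there as an item of its own, apart from rehospitalization. A further secondary objective is general: "Assess eventual complications 30 days after hospital discharge". Under Additional Information, the Substudy aims to "Determine the association between different variables, complication rate and mortality 30 days after discharge", again with complications apart from mortality.

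The data for these aims come from the form set out under Specific Protocol (Operational Definition of Variables). Its Follow-up part asks two outcome questions:

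- **Re-admission.** It opens with "Re-internment Yes No" and then asks the cause: heart failure, respiratory insufficiency, renal insufficiency, sepsis or other. Sepsis has a sub-item, "Sepsis Yes: Sepsis starting point: Mediastinitis or other focus". There is also a line for "Another cause of re-admission".
- **Death.** Yes or no within 30 days after discharge, then "Cause of death in follow-up: Cardiovascular- NON-cardiovascular cause".

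The itemised complications (wound, sternal, urinary and respiratory infection, mediastinitis, stroke, atrial fibrillation, renal failure and others) are in the Postoperative part. It precedes the length-of-stay and discharge-status fields.

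**The concern.** The objectives speak of complications in general and of infection in particular, while the form sees an event after discharge only if it led to re-admission or death. Patients treated in clinic or at home for a wound infection, an arrhythmia or a minor bleed would be counted as free of complications.

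Two things are at stake. A published 30-day complication or infection rate would be read as covering all such events when it does not. And the variables found to be associated with complications would really be associated with death or re-admission, which also depends on the threshold for admitting a patient. An analysis plan can define endpoints from the fields collected, but it cannot supply an event that nobody asked about.

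**Working it through.** The protocol gives no figure on this point to reproduce. The check sets each promised 30-day outcome against the Follow-up fields.

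| Promised for the 30 days after discharge | Field on the Follow-up form | Captured? |
|---|---|---|
| All-cause mortality | Death yes/no | Fully |
| Cardiovascular mortality | Death, cardiovascular or not | Fully |
| Rehospitalization | Re-admission yes/no, with cause | Fully |
| Infectious complications | Sepsis with focus as a cause of re-admission, or the other-cause line | In part |
| Complications in general (last secondary objective, Substudy) | Only those that caused re-admission or death | In part |

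**Infection, case by case.**

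1. Re-admitted with sepsis: recorded, with focus.
2. Re-admitted with an infection not classed as sepsis: recorded under other causes and recoverable from the free text. The Postoperative part defines sepsis as "Suspected or documented infection with dysfunction of target organ" plus further criteria. If that definition carries over to follow-up, which the protocol does not say, a wound infection without organ dysfunction falls here.
3. Treated without re-admission: no field.
4. Fatal without re-admission: recorded only as a non-cardiovascular death. For deaths in hospital, by contrast, the Discharge part offers an infectious cause.

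**Do the Postoperative items extend past discharge?** Their place on the form, before discharge status, says not, and the COVID-19 item there is limited to the hospital stay.

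**How many patients could still be asked more?** Inputs: enrolment from 1 October 2020 to 30 September 2021 (365 days) and protocol version date 8 July 2021. Assumptions: even accrual, 14 days from enrolment to discharge, in-hospital deaths ignored.

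- Items in use on 8 July 2021: the contact is still to come if discharge is on or after 8 June. From 8 June to 30 September is 23 + 31 + 31 + 30 = 115 days. Adding the 14-day stay gives 129 enrolment days, and 129/365 = 35.3%.
- Items in use 30 days later: 129 − 30 = 99 days, and 99/365 = 27.1%.
- With 2000 to 3000 patients: 0.271 × 2000 ≈ 542 at the low end and 0.353 × 3000 ≈ 1060 at the high end.

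Each further day of delay removes about 1/365, or 0.27 percentage points.

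**The case against.** The strongest reply is that the protocol's own wording counts death and re-admission among the complications, so the infectious outcome may mean only infections behind those events. On that reading, form and objective largely agree and the fault is loose wording. This is a fair reading of the four-item list. It does not cover the separate general objective or the Substudy, neither of which is limited to re-admission. If the narrow reading is what the sponsor meant, saying so settles the matter.

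A second reply is that the 30-day stage refers to forms in the plural, so another form might exist. None is shown, and its existence would be a guess.

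A reader might also infer more than the protocol supports:

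- *That infections after discharge go unrecorded.* Those leading to re-admission are recorded as sepsis or can be found in the free text.
- *That infections are the events most undercounted.* The protocol gives no rates, and outpatient arrhythmia could be missed as often.
- *That the number of missed events can be stated.* It depends on the true rate and on the share treated without re-admission, and the protocol gives neither.
- *That the missed events are lost for good.* The form collects telephone numbers and e-mail, so patients already contacted might be reached again.
- *That the primary objectives fail.* In-hospital complications (1.a) are itemised and re-admission (1.b) is recorded.

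**Conclusion.** The point holds as a mismatch between objectives and data collection, fixed in the protocol itself. Followed as written, the 30-day complication rate is a death-or-re-admission rate, and infection is captured in part. The direction of the error is an undercount. Its size cannot be estimated from the protocol. It touches two secondary objectives and the Substudy, and leaves the primary objectives and three of the four named outcomes intact. It is a matter to consider, not a threat to the registry. The conclusion rests on the form as shown being the whole of the 30-day data collection.

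**What to change.** **For all patients.** In the secondary objectives and the Substudy, restate the 30-day outcome as death or re-admission by cause within 30 days of discharge, and restate infectious complications as infection leading to re-admission. The restated infection outcome needs the other-cause free text to be read for infections. Fatal infections without re-admission would stay within non-cardiovascular death. The cost is a change of wording and a narrower promise.

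**Where the 30-day contact is still to come.** Add a few Yes/No items asked whether or not the patient was re-admitted: wound or sternal infection or mediastinitis, stroke or transient ischaemic attack, infarction, bleeding, and arrhythmia. Define each as new since discharge. Report them separately and descriptively, without pooling them with the main outcome, because they would cover only the late-enrolled 27% to 35% under the assumptions above. The cost is a slightly longer contact.

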The principal investigators of the study are:

[name]

[name]

It will be assigned during the inclusion of investigator patients for each of the centers, who will be responsible for completing the form (*CRF*) and sending the registered data.

7

Additional Information

Introduction

More than ten years have passed since the last CCV registration in the Argentine Republic

In recent decades, the evolution of CCV has shown a reduction in the rate of complications and mortality in centers

specialized

objectives

Record

1. determine complications, mortality and hospital stay, as well as evolution at 30 days after CVD

In our country

2. Compare our variables with those exposed by the different international scores and thus be able to predict the

estimated evolution of our patients.

Substudy

1. Determine the association between different variables, complication rate and mortality 30 days after discharge.

Proposed design

The study consists of **2 stages** , with the voluntary participation of the different centers, which is divided into nosocomial phase and phase a

30 days after discharge

Prospective multicenter registry of prognostic correlation with various risk scores in patients undergoing CCV and

evolution of the same 30 days after discharge

Material and methods

Patients who meet the eligibility criteria described above are included from October 1, 2020

The protocol consists of 2 stages:

1) Nosocomial Phase: a descriptive record is made of the referred variables and the risk parameters upon discharge from

the patients

2) 30 days after discharge, the respective forms will be filled out for the final evaluation of patients who have undergone CCV and discharged from participating institutions

8

Specific Protocol (Operational Definition of Variables):

A complete clinical history of the patient is taken (according to usual practice) and the data is filled out in the Pre, Intra and Post-surgical stage according to what is established in the form

Affiliate Information and Background

Record ID _____

Date of admission _____

Acronyms for Name and Surname _____

Last 3 digits of document number _____

(Last 3 digits only)

Age _____ gender _____ Weight (kg) _____ Height (cm) _____

Public Hospital Coverage

PAMI

Social work

Prepaid

Particular

Telephone

Phone 2 _____

Email _____

Background

Arterial hypertension Yes No

Diabetes Yes No

Diabetic retinopathy Yes No

Dyslipidemia Yes No

Ex-smoker tobacco

I never smoke

Smokes daily

Smokes occasionally

It is unknown

9

Hyperuricemia Yes No

HIV Yes No

Systolic LV dysfunction Yes No

Heart failure Yes No

Myocardial infarction No <30 days> 30 days

Myocardial revascularization surgery Yes No

Valve surgery Yes No

Other cardiovascular surgery Yes No

Type of cardiovascular surgery

(Describe ...)

Coronary angioplasty Yes No

Immunocompromise Yes No

Mediastinal radiation Yes No

Stable chronic angina Yes No

Chronic atrial fibrillation Yes

No

Unstable angina Yes No

Family history of coronary disease Yes No

Peripheral vascular disease Yes No

Pulmonary Hypertension Yes No

Cerebrovascular disease Yes No

Syncope Yes No

SAHOS Yes No

COPD No

Mild

Moderate

Severe

It is unknown

Remote Non-Recent Pneumonia
It is unknown
Did you have COVID-19 within the month prior to surgery? If not
Liver disease Yes No
Illicit drug use No Recent Remote
It is unknown
Alcohol abuse No
<1 glass per day
2 to 7 glasses per day
> 7 glasses per day
It is unknown
Usual medication Aspirin

10
Clopidogrel
Ticagrelor
Prasugrel
Statins
Beta-blockers
ACEI
ARA-II
Loop diuretics
Thiazides
Spirinolactone
Insulin
Oral hypoglycemic
Anticoagulants
Suspension P2Y12 Inhibitors Yes No
Days of suspension of Inhibitors P2Y12

Frail patient Yes No
I use a fragility score Yes No
Fragility score

Other background

Presurgical data

Presurgical diagnosis Heart failure
Endocarditis
Acute aortic syndrome
Ischemic heart disease
Valvular disease
Pericardial involvement
Other
Related signs and symptoms Dyspnoea
Precordial pain
Edema in lower limbs
Febrile syndrome
Syncope
Palpitations
Neurological focus
Acute Pulmonary Edema
Tachyarrhythmias
Bradyarrhythmias
Other

eleven
(Select at least one)
Coronary heart disease Yes
No
Left Coronary Trunk Injury Yes

No

Number of glasses _____

Vessels affected Descending Anterior _____

Diagonal _____

Circumflex _____

Lateroventricular _____

Right Coronary _____

Other _____

Valvular disease Yes _____

No _____

Type of valve pathology Aortic stenosis _____

Aortic insufficiency _____

Mitral stenosis _____

Mitral Insufficiency _____

Pulmonary stenosis _____

Pulmonary insufficiency _____

Tricuspid stenosis _____

Tricuspid Insufficiency _____

(Select at least one)

Combined Surgery Yes _____

No _____

(Valular + Bridges)

Type of procedure Scheduled _____

Urgency _____

Emergency _____

Laboratory upon admission

Hematocrit _____ Leukocytes _____ Platelets _____

Blood glucose _____ Uremia _____ Creatinine _____

Cholesterol _____ HDL _____ LDL _____

Triglycerides _____ Total bile _____ GOT _____

GPT _____

Electrocardiogram

Rhythm _____ Frequency _____

Prolonged PR _____ AV block _____

Right bundle branch block _____ Left bundle branch block _____

ST elevation _____ ST elevation _____

12

T wave inversion _____

SCORES

We ask you to complete the following values by calculating them. Click on the following links to enter the respective online calculators:

EUROSCORE: <https://www.rccc.eu/Cardio/euroscoreII.html>

ARGENSCORE: <http://argenscore.org/calculadora.aspx>

EUROSCORE II mortality (%) _____

ARGENSCORE score _____

ARGENSCORE Mortality _____

Use of pre-surgical IACB Yes No

Use of Swan Ganz presurgical Yes No

Use of presurgical inotropics Yes No

Intraoperative

Date of surgery _____

Patient condition Stable Unstable _____

Use of ventricular assist Yes No

Use of BCIAo Yes No

Required transfusion of blood products Yes No

Red blood cells _____

(Units)

Platelets _____

(Units)

Plasma

(Units)

Extracorporeal circulation Yes No
CEC time

(Minutes)

Clamping time

(Minutes)

CRM was carried out Yes No
Left breast bridge Yes No
Right breast bridge Yes No
Radial bridge Yes No
Number of radial bridges

Page 13

13

Venous bridge Yes No
Number of venous bridges

Endarterectomy Yes No

Quality of the distal beds Good Regular
Bad

Valve surgery was performed Yes No

Aortic valve plastic Yes No

Aortica Jacoub plastic technique

David

Aortic valve replacement Yes No

Type of Biological Aortic Valve with stent

Biological without stent

Single Disc Mechanics

Clamshell Mechanics

Biological valve type Aortic Pericardial

Swine

Bovine

Aortic biological valve measurement

(Number)

Brand of Aortic Biological Valve

Aortic mechanical valve measurement

(Number)

Aortica mechanical valve brand

Ring enlargement Yes No

Ring enlargement technique

Plastic Mitral Valve Yes No

Plastic was made on the previous valve

Posterior leaflet

Mitral valve replacement Yes No

Biological Mitral Valve Type with Stent

Biological without stent

Single Disc Mechanics

Clamshell Mechanics

Type of Mitral Pericardial Biological Valve

Swine

Page 14

14

Bovine

Mitral biological valve measurement

(Number)

Mitral Biological Valve Brand

Mitral mechanical valve measurement

(Number)

Mitral mechanical valve brand

Intra-operative TEE in mitral surgery Yes No

Plastic Tricuspid Valve Yes No

Tricuspid valve replacement Yes No

Biological Tricuspid Valve Type

Mechanics

Tricuspid biological valve measurement

(Number)

Brand of Tricuspid Biological Valve

Tricuspid mechanical valve measurement

(Number)

Tricuspid mechanical valve brand

Pulmonary valve plastic Yes No

Pulmonary valve replacement Yes No

Biological Pulmonary Valve Type

Mechanics

Pulmonary biological valve measurement

(Number)

Pulmonary biological valve brand

Pulmonary mechanical valve measurement

(Number)

Pulmonary mechanical valve brand

Ross Surgery Yes No

Page 15

fifteen

Ascending Aortic Surgery Yes No

Type of Ascending Aorta Surgery Bentall de Bono

Resuspension

WHEAT (supracoronary)

Tirone David

Yacoub

Cabrol

Tubular portion replacement

Reattachment of supra-aortic vessels

Other

Aortic prosthesis placement Yes No

Aortic prosthesis measurement

(Number)

Intra-surgical hemorrhage Yes No

Cause of Medical Surgical Bleeding

Intra-surgical arrest Yes No

Readmission to CEC Yes No

Other complications

Postoperative

Via air Fast track (extubate)

Intubated
Extubates at <6 hours
6 to 12 hours
12 to 24 hours
> 24 hours
Long ARM Yes No
ARM days

Reintubation Yes No
Hemorrhage Yes No
(> 500 ml in the 1st hour or> 400 ml in the 2nd hour or
> 300 ml in the 3rd hour or> 200 ml in the 4th hour or
> 100 ml in the 5th hour)
Type of Hemorrhage Medical Surgical
Surgical examination required Yes No
Surgical resolution Yes No
Transfusion of blood products Yes No
Right Ventricular Dysfunction Yes No
(Persistent arterial hypotension, blood pressures

16

Elevated ventricular (right atrium) filling,
low cost with need for intervention
pharmacological and eventually mechanical (TAPSE <17
mm or visual impression by Echocardiography of
RV dysfunction))
Low expenditure syndrome Yes No
(Systolic blood pressure <90 mmHg, pale and
skin coldness, lack of capillary filling,
clouding and oliguria, heart index
<2.2
L / min / m², pulmonary capillary pressure> 18 mmHg, with
inotropic and / or balloon requirement
intra-aortic counterpulsation (IACAB))
Inotropic / vasopressor requirement Yes No
Inotropics / Vasopressors used Dopamine
Dobutamine
Milrinone
Levosinmendan
Noradrenaline
Vasopressin
Adrenalin
Swan Ganz requirement Yes No
Perioperative myocardial infarction Yes No
Definition of perioperative infarction according to the center Development of Q waves
per ... Increased CPK MB \hat{a} % \neq 80 IU / ml
Parietal alterations on echocardiogram
Troponin T or I> 10 times its baseline value
US troponin> 10 times baseline
Atrial fibrillation Yes No
Atrioventricular block Yes No
Complex ventricular arrhythmia Yes No
Transient pacemaker Yes No
Permanent pacemaker Yes No
I do prophylaxis for postoperative AF Yes No
Drug used

POP day of initiation of prophylaxis for AF

Renal failure Yes No
(Increase in creatinine above 50%
with respect to the baseline value and / or

17

hemodialysis)

Hemodialysis Yes No

Stroke Yes No

(Focal and / or diffuse brain injury confirmed by clinical findings and / or computed tomography with sensory or motor sequelae upon discharge of the patient)

Transient ischemic accident Yes No

Psychiatric disorders Yes No

(Any of the following: delirium, hallucinations, psychomotor arousal)

Required treatment with ... Risperidone

Quetiapine

Haloperidol

Other

Respiratory distress syndrome Yes No

(Infiltrate in 4 quadrants - PCP <18 - PAFI <200)

Fever without obvious focus Yes No

Sepsis Yes No

(Suspected or documented infection with dysfunction of target organ and at least two of the following criteria: Temperature > 38 ° C or <36 ° C, White blood cell count greater than 12,000 uL or less at 4000 uL, Tachycardia, Tachypnea > 30 rpm, Altered mental state, Positive culture of primary focus of infection, mean arterial pressure less than 70 mm Hg for a minimum fingers

hours, poor distal perfusion ("))

Urinary infection Yes No

Respiratory infection Yes No

Surgical wound infection Yes No

Superficial wound infection Yes No

Saphenous wound infection Yes No

Sternal infection Yes No

Mediastinitis Yes No

Sternal reopening requirement Yes No

Sternal reopening POP day

Sternal mechanical instability Yes No

COVID-19 infection development during internment

18

If not

TOTAL days of hospitalization until discharge

POSTOPERATIVE days until discharge

Discharge

Alive

Dead _____

Death cause:

Infectious

Cardiovascular

Distributive shock

Hemorrhage

Cardiac tamponade

Stroke

Respiratory distress

Multi-organ failure

Another cause

Death from infectious cause: Mediastinitis Pneumopathy Sepsis Other

Identified germ

Death from cardiovascular cause: Myocardial infarction Arrhythmia Heart failure

Pre Registration Laboratory

Hematocrit _____ Blood glucose _____

Uremia _____ Creatinine _____

Medication at discharge ASA

Clopidogrel

Ticagrelor

Prasugrel

Statins

Beta-blockers

Sartan

ACE inhibitors

Loop diuretic

Thiazide

Spironolactone

Insulin

Oral hypoglycemic

Anticoagulants

Investigator Notes

19

Follow-up

Re-internment Yes No

(Within the first 30 days after discharge)

Cause of re-admission:

Heart failure

Respiratory insufficiency

Renal insufficiency

Sepsis:

Other

Sepsis Yes: Sepsis starting point: Mediastinitis or other focus

Another cause of re-admission

Death no

Death Yes:

(Within the first 30 days after discharge)

Cause of death in follow-up: Cardiovascular- NON-cardiovascular cause
